13.3.4.2 Examination of Subgroups

Important demographic and baseline value-defined subgroups may be investigated.

Subgroups or alternate imputations to investigate the impact of the COVID-19 pandemic on the analyses due to an expected increased number of subjects with missing data will also be investigated.

A detailed description will be provided in the Statistical Analysis Plan.

13.4 Safety Analysis

13.4.1 Adverse Events

An overview of all treatment-emerging AEs including severity, relationship to IMP, serious AEs (SAEs) and AEs leading to withdrawals of treatment and withdrawal from trial or death will be presented by treatment group.

AEs will be summarised by treatment group, system organ class (according to MedDRA), and preferred term (according to MedDRA) displaying number of subjects in treatment group, number and percentage of subjects having the AE as well as number of AEs. Furthermore, AEs will be summarised according to severity, relationship, outcome, and seriousness.

SAEs and AEs leading to withdrawal from treatment will be listed and tabulated, if appropriate.

Clinical Trial Protocol

Vicore Pharma AB
Trial ID: VP-C21-005

Version: 7.0
Date: 15-Sep-2021

13.4.2 **Electrocardiogram**

12-lead ECG data will be summarised by visit including the change from baseline. The number of abnormal assessments will be summarised by visit and for changes from baseline to end-of-trial.

13.4.3 **Vital Signs**

Vital signs data (blood pressure and pulse) will be summarised by visit including the change from baseline.

13.4.4 **Laboratory Safety Assessments**

Continuous laboratory data will be summarised by visit including the change from baseline. Categorical data will be summarised by visit using frequency and percentages. Laboratory parameters will be categorised as ‘low’, ‘normal’ or ‘high’ (*i.e.* below, within, or above the reference ranges, respectively) and summarised by visit and for changes from baseline to end-of-trial in a shift table.

13.4.5 **Physical examination**

Abnormal findings on the physical examination will be summarised by visit.

14 **INDEPENDENT DATA MONITORING COMMITTEE**

An independent data monitoring committee (IDMC) has been established and will have their first meeting before the trial starts.

The functions and responsibilities of the IDMC is described in an IDMC charter.

Throughout the duration of the trial, the IDMC will evaluate all SAEs on an ongoing basis.

Further, the IDMC will monitor the overall safety of the trial during regular meetings and provide appropriate written recommendations to the Sponsor regarding trial continuation, protocol modifications or trial suspension.

Any safety related IDMC recommendations that may result in protocol changes or to the management of subjects in the trial will be reported to the Competent Authorities (CAs) and IECs. A letter of trial continuation after each IDMC meeting will be supplied to the CAs and IECs if required.

15 **GOOD CLINICAL PRACTICE**

This trial will be carried out in compliance with the protocol, ICH-GCP R2, Standard Operating Procedures of the CROs and applicable regulatory requirements.

The investigator agrees, when signing this protocol, to adhere to the instructions and procedures described in it, to the principles of the Declaration of Helsinki, ICH-GCP R2 and applicable regulatory requirements.

Clinical Trial Protocol

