4.4 Primary Endpoint

Nature and frequency of adverse events occurring over the trial period.

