5.6 Withdrawal Criteria

5.6.1 Evaluation for Withdrawal after each 12 Week Treatment Period

After completion of each 12-week treatment period, the investigator will make a medical evaluation and decide if the subject may continue into the next 12-week treatment period. The decision will be based on:

- No immediate need for other antifibrotics
- A positive risk/benefit balance

Clinical Trial Protocol

Vicore Pharma AB
Trial ID: VP-C21-005

Version: 7.0
Date: 15-Sep-2021

Failure to pass the medical evaluation will result in the subject being withdrawn from the trial (see Section 5.4.2).

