5.7 Withdrawal from Trial

A subject will be withdrawn from trial if any of the following occurs:

- A decline from baseline in FVC value of > 10% predicted on 2 consecutive occasions and an FVC <60% predicted (*Specific for UK*: FVC <80 % predicted ; or FVC <60% predicted for subjects previously treated with nintedanib and/or pirfenidone, or refused such treatments)
- A decline from baseline in FVC value of 5-10% predicted on 2 consecutive occasions and worsening of respiratory symptoms and FVC <60% predicted (*Specific for UK*: FVC <80 % predicted; or FVC <60% predicted for subjects previously treated with nintedanib and/or pirfenidone, or refused such treatments)
- Consistent failure to comply with dietary requirements in Section 5.4, according to the investigators
- The investigator judges it necessary due to medical reasons
- Failure to pass the medical evaluation after each 12-week treatment period (see Section 5.6.1)
- It is the wish of the subject to withdraw for any reason
- Pregnancy

An end-of-trial visit (Visit 15) must be completed for all subjects withdrawn from the trial.

Subjects withdrawn due to pregnancy will be followed – as consented to – until termination or delivery and the infant must be followed at least until the age of one month.

Subject who withdraws prior to week 12 will be replaced until 60 subjects have completed the 12-week visit.

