6 TRIAL DESIGN

6.1 Overall Trial Design

This is a multi-centre, open-label, single-arm trial investigating the safety and efficacy of C21 in which subjects with IPF will be treated for a maximum of 36 weeks. In total, approximately 60 subjects will be recruited.

To ensure careful and ongoing evaluation of the individual risk/benefit profiles, each subject will undergo a medical evaluation by the investigator at the end of every 12-week treatment period, where the investigator will evaluate if continuation into the next 12-week treatment period is considered safe for the individual subject.

In addition, throughout the duration of the trial, an independent data monitoring committee (IDMC) will evaluate all serious adverse events (SAEs) on an ongoing basis in accordance with the IDMC charter. The IDMC will monitor all available safety data during regular meetings as

Clinical Trial Protocol

Vicore Pharma AB
Trial ID: VP-C21-005

Version: 7.0
Date: 15-Sep-2021

defined in the IDMC charter and provide appropriate recommendations to the Sponsor on the overall safety of trial participants (see Section 14).

The subjects will attend up to 15 visits to the clinic:

- Visit 1: Screening
- Visits 2 – 7: Treatment period 1
- Visits 8 – 11: Treatment period 2
- Visits 12 – 14: Treatment period 3
- Visit 15: End-of-trial

IMP will be administered as home treatment twice daily (*b.i.d.*) during all treatment periods 1-3.

Final safety follow-up assessments at Visit 15 (end of trial visit), must be performed for all subjects who have received trial treatment. Visit 15 must be scheduled 2-4 weeks after the last IMP administration (see Section 7.3).

The maximum duration of the trial for any subject will be approximately 44 weeks, including a screening period of up 4 weeks, a treatment period up to 36 weeks and a visit for safety follow up to be conducted maximum 4 weeks after the last dose of IMP (please see clinical trial design in Figure 1).

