6.5.2 Treatment Periods (Visits 2-14)

The total treatment period may last for maximum 36 weeks, comprising three 12 week treatment periods. At the end of treatment period 1 (Visit 7) and treatment period 2 (Visit 11), a medical evaluation is performed by the investigator to assess if treatment can be continued for an additional 12 weeks (see Section 5.4.1)

- Treatment period 1 (Visit 2-7)
 - Subjects will attend the clinic every 2 weeks for the first 6 weeks (Visit 2-5) and subsequently every 3 weeks for the last 6 weeks (Visit 6-7)
- Treatment period 2 (Visit 8-11)
 - Subjects will attend the clinic every 3 weeks for 12 weeks (visit 8-11)
- Treatment period 3 (Visit 12-14)
 - Subjects will attend the clinic every 4 weeks for 12 weeks (Visit 12-14)

The procedures to be performed at each visit are specified below.

Visit 2

Clinical Trial Protocol

Vicore Pharma AB
Trial ID: VP-C21-005

Version: 7.0
Date: 15-Sep-2021

Visit 2 can be scheduled as soon as the relevant screening assessments are available. Visit 2 must occur 3-30 days from Visit 1 (screening) to ensure that no eligibility assessments are older than 30 days when treatment is initiated.

The following procedures are performed:

- Re-evaluation of in- & exclusion criteria (including physical examination, assessment of vital signs, ECG, spirometry, slit lamp and laboratory results from Visit 1)
- Concomitant medication
- Pregnancy testing (beta-HCG)
- Assignment of enrollment number
- 12-lead ECG
- Holter ECG
- Blood sampling for safety and biomarker assessments (See [Table 1](#) and [Section 8](#))
- Urinanalysis (dipstick for bilirubin, glucose, ketones, protein, specific gravity, urobilinogen and pH)
- Spirometry
- IMP administration
- PK sampling
- Hand-out of medication
- Re-instructions regarding dietary restrictions prior to IMP administration (see [Section 5.4](#))
- Reporting of AEs

Visits 3-14

- Concomitant medication
- Pregnancy testing (urine dipstick)
- Physical examination, (including body weight and vital signs)
- Blood sampling for safety
- 12-lead ECG
- Urinanalysis (dipstick for bilirubin, glucose, ketones, protein, specific gravity, urobilinogen and pH)
- Spirometry
- Return of medication
- IMP compliance check
- Drug accountability
- Hand-out of medication (not applicable for visit 14)
- Re-instructions regarding dietary restrictions prior to IMP administration (see [Section 5.4](#).
Not applicable for visit 14)
- Reporting of AEs

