8.2 Safety Assessments

8.2.1 Adverse Events

Adverse events (AEs) will be reported from signing of informed consent until end-of-trial participation (Visit 15).

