13.1 Sample Size and Power Considerations

Sample size is based on assumptions of a 40 mL decline in FVC/24 weeks and a standard deviation of 200 mL. With 55 evaluable subjects there is a 90% power that the 90% confidence interval for the decline in FVC at 24 weeks exclude the value 120 mL, a value considered to represent the natural course decline in 24 weeks for an untreated subject. The total of 60 subjects will be included to compensate non-evaluable subjects for reasons such as early drop out.

Analysis Data Sets

The full analysis set (FAS) will consist of all subjects who have received at least one dose of IMP and who has at least one post-baseline assessment of efficacy.

The per protocol analysis set (PPAS) will be a subset of FAS and consist of all subjects without any major protocol deviations that are judged to compromise the analysis of the data and with data collection up to at least week 24. All protocol deviations will be judged as major or minor prior to database lock.

The safety analysis set (SAS) will consist of all subjects who have received at least one dose of IMP.

The pharmacokinetic (PK) dataset will consist of all subjects selected for PK assessments and with at least one post-dose plasma sample analysed.

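### AE frequency, the primary endpoint, is planned only as crude percentages and event counts although exposure can run from one dose to 36 weeks; read as 36-week risks, the percentages can understate.

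*Combined protocol and SAP*

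**What the plan says.** The primary endpoint (Section 4.4) is "Nature and frequency of adverse events occurring over the trial period". Section 13.4.1 reports it by system organ class and preferred term as the "number and percentage of subjects having the AE as well as number of AEs", with breakdowns by severity, relationship, outcome and seriousness. The denominator comes from Section 13.1: "The safety analysis set (SAS) will consist of all subjects who have received at least one dose of IMP".

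Length of exposure is not fixed:

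- Section 6.1: "subjects with IPF will be treated for a maximum of 36 weeks".
- Section 6.5.2: "The total treatment period may last for maximum 36 weeks, comprising three 12 week treatment periods". A medical evaluation takes place at weeks 12 and 24.
- Section 5.6.1: "Failure to pass the medical evaluation will result in the subject being withdrawn from the trial".
- Section 5.7 adds withdrawal rules based on FVC and other grounds, then: "Subject who withdraws prior to week 12 will be replaced until 60 subjects have completed the 12-week visit".

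AEs are collected from consent to Visit 15 (Section 8.2.1), which falls 2-4 weeks after the last dose, also for withdrawn subjects (Section 6.5.3). Safety summaries are not imputed (Section 13.3.4.1). Section 13 describes itself as the principal features and leaves detail to a separate SAP; the document reviewed contains no such SAP text.

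**The concern.** A simple percentage gives a subject followed for four weeks the same weight as one followed for 36. Replacement adds to this: each subject lost before week 12 stays in the safety set and another is enrolled, so short exposures accumulate in the denominator. A count of events does not help without the time over which they were counted.

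Safety is the primary objective, and Section 3.6 says that the data will guide further C21 trials. Repeated dosing in the Phase 1 trials lasted at most 8 days (Section 3.5), so how risk builds up over months is much of what this trial can add. There is no concurrent arm with the same withdrawal pattern against which to read the percentages. For FVC, a secondary endpoint, the plan deals with early withdrawal through week-24 imputation and a mixed model. For the primary endpoint, Section 13.4 contains nothing comparable.

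**Working it through.** **The plan's own figures.** The only sample-size calculation concerns FVC; none is given for AEs. With a difference of 120 - 40 = 80 mL, SD 200 mL and a two-sided 90% CI, n = (200 × (1.645 + 1.282) / 80)² = 53.5. An exact t calculation at 55 gives 90.05% power, so the stated 55 reproduces. Enrolling 60 for 55 evaluable implies a loss of 5/60 = 8.3%, the only loss figure in the document. It is not split by time or reason.

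**Model.** Let R be the true 36-week risk of a first AE. Assume a constant hazard, withdrawal unrelated to the AE, and on-treatment events only. A subject exposed for t weeks has a first event with probability 1 - (1 - R)^(t/36). The crude percentage is the average of this over the exposure mix. Early losses are placed at week 6 (assumed); the others fall at weeks 12 and 24, each a share of those still on treatment.

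For R = 50% the probabilities at 6, 12, 24 and 36 weeks are 10.9%, 20.6%, 37.0% and 50%. With 10% lost at each stage, the shares of dosed subjects are 0.100, 0.090, 0.081 and 0.729, so

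0.100 × 0.109 + 0.090 × 0.206 + 0.081 × 0.370 + 0.729 × 0.500 = 0.424.

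Mean exposure is 0.100 × 6 + 0.090 × 12 + 0.081 × 24 + 0.729 × 36 = 29.9 weeks. The other mixes follow in the same way; the loss rates are assumptions except the 8.3%.

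| Lost before wk 12 / at wk 12 / at wk 24 | Complete wk 36 | Mean exposure (weeks) | True 50% appears as | True 20% appears as |
|---|---|---|---|---|
| 8.3% / 0 / 0 | 91.7% | 33.5 | 46.7% | 18.6% |
| 10% / 10% / 10% | 72.9% | 29.9 | 42.4% | 16.7% |
| 10% / 20% / 15% | 61.2% | 27.4 | 39.4% | 15.4% |
| 20% / 20% / 20% | 51.2% | 24.6 | 35.8% | 13.9% |

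**Relaxing the assumptions.**

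- *Post-dose window counted at the same hazard.* In the 10/10/10 mix a true 50% appears as 44.6% with 2 weeks and 46.7% with 4. In the 8.3% mix with 3 weeks, 50% appears as 49.7% and 20% as 20.1%. If everyone completes and 4 weeks count, a true 20% appears as 22.0%, an overstatement.
- *Early risk.* If all risk falls in the first 6 weeks and nobody stops before then, crude equals true.
- *The AE causes the stop.* If it is the only cause, crude equals true. Unrelated losses of 10% or 20% at weeks 12 and 24 bring the ratio of crude to true down to 0.91 or 0.82.
- *Informative withdrawal.* Take 68 dosed subjects: 8 stopping at each of weeks 6, 12 and 24, and 44 completing. If those who stop have twice the hazard of completers (whose 36-week risk is 20%), the crude figure is 18.4%, the exposure-adjusted estimate 23.1% and the true 36-week risk 25.7%. Adjustment narrows the gap without closing it.

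**The case against.** The strongest reply is that the endpoint is frequency over the trial period, not a 36-week risk. The percentage of dosed subjects with an AE describes that validly, and is an underestimate only of a quantity that the protocol does not name. This stands: the gap is in interpretation, not an error in the endpoint.

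A reader might infer that the reported frequencies will certainly understate the 36-week risk. The document does not support that. It gives no withdrawal rates by time and does not define treatment-emergent, so how much of the post-dose window counts is open. The checks above include cases with no bias and one with overstatement, and the 8.3% allowance alone produces little.

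A reader might also infer that time at risk enters no AE analysis at all. That holds for the protocol text only. Section 13 defers detail to the SAP, where exposure tables could appear, and Section 13.4 does show ECG, vital signs, laboratory values and physical findings by visit. Still, whether time at risk enters the summary of the primary endpoint is a principal feature, and deferral is no reason to leave it unstated.

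Finally, patient-year rates have their own weakness. With early-onset risk in the 68-subject mix above, extrapolating a constant rate to 36 weeks gives 26.7% against a true 20%. That is a reason to pair them with cumulative incidence. No between-arm comparison, decision rule or sample size depends on these percentages, which limits the consequences.

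**Conclusion.** The point holds as a gap in interpretability. Section 13.4.1 plans percentages and event counts over all dosed subjects, and nothing in Section 13.4 lets a reader relate them to exposure that can run from one dose to 36 weeks. Taken as risks over the full course, the percentages can understate: a true 50% would appear as 47% to 36%, and a true 20% as 19% to 14%, across losses from 8.3% at week 6 alone to 20% at each stage. Those figures rest on a constant hazard, withdrawal unrelated to the AE, and no post-dose window. Understatement is likely where withdrawal is appreciable and unrelated to the AE, but neither its size nor its direction is fixed by the document. The planned AE tables would not show which case applies. This is a cheap improvement to the primary analysis; the FVC sample size is unaffected.

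**What to change.** In Section 13.4.1, carried into the SAP before database lock, keep the crude table and add an extent-of-exposure table. For overall treatment-emergent AEs, SAEs, related AEs, and the cardiac and ophthalmic AEs of special interest (Section 9.3), also add:

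- (a) subjects with a first event per 100 patient-years at risk, with a 95% CI, stating whether the at-risk window ends at the last dose or at Visit 15;
- (b) cumulative incidence at weeks 12, 24 and 36 with numbers at risk, treating death as a competing event and withdrawal as censoring, with the caveat that withdrawal may be informative.

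The cost is a few tables from dates already collected. The AE figures may look somewhat higher. The rates in (a) assume a roughly constant hazard, so they should be read together with (b).

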	
pattern (if no previous computed tomography is available, the qualifier “new” can be dropped)
 
• Deterioration not fully explained by cardiac failure or fluid overload
5)	Concurrent serious medical condition with special attention to cardiac or ophthalmic conditions (e.g. contraindications to cataract surgery), or moderate to severe hepatic impairment, which in the opinion of the investigator makes the subject inappropriate for this trial
6)	Malignancy within the past 5 years with the exception of in situ removal of basal cell carcinoma and cervical intraepithelial neoplasia grade I
7)	Treatment with any of the medications listed below within 4 weeks prior to Visit 1: 
• Strong Cytochrome p450 (CYP) 3A4 inducers (e.g. rifampicin, phenytoin, St. John’s Wort)• Strong CYP3A4 inhibitors (e.g. clarithromycin, ketoconazole, nefazodone, itraconazole, ritonavir)• Medicines that are substrates of CYP1A2, CYP3A4 or CYP2C9 with a narrow therapeutic range• Experimental drugs• Antifibrotic treatment• Any systemic immunosuppressive therapies other than:
◦ Inhaled corticosteroids which can be used throughout the trial period provided the dose is kept stable◦ Corticosteroids for the treatment of acute exacerbations◦ The continuation of stable doses of ≤ 15 mg daily doses of prednisolone or equivalent
8)	Treatment with any of the medications listed below within 2 weeks prior to Visit 1: 
◦ Proton pump inhibitors (PPIs) more than once daily◦ Histamine H₂ receptor antagonists (H₂RA)◦ Sulphasalazine and rosuvastatin◦ High dose breast cancer resistance protein sensitive substrates (other than sulphasalazine or rosuvastatin)
9)	Any of the following findings at Visit 1: 
◦ Prolonged QTcF (QT interval with Fridericia’s correction) (>450 ms), clinically significant cardiac arrhythmias or any other clinically significant abnormalities in the resting ECG, as judged by the investigator◦ Increased AST or ALT >3 times upper limit of normal (ULN), or bilirubin >1.5 times ULN◦ Positive results for hepatitis B surface antigen (HBsAg), hepatitis C virus antibody (HCVAb) or human immunodeficiency virus 1+2 antigen/antibody (HIV 1+2 Ag/Ab)◦ Positive serum pregnancy test (minimum sensitivity 25 IU/L or equivalent units of human chorionic gonadotropin [HCG])

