- Prolonged QTcF (QT interval with Fridericia's correction) (>450 ms), clinically significant cardiac arrhythmias or any other clinically significant abnormalities in the resting ECG, as judged by the investigator
- Increased AST or ALT >3 times Upper Limit of Normal (ULN), or bilirubin >1.5 times ULN
- Positive results for hepatitis B surface antigen (HBsAg), hepatitis C virus antibody (HCVAb) or human immunodeficiency virus 1+2 antigen/antibody (HIV 1+2 Ag/Ab)
- Positive serum pregnancy test (minimum sensitivity 25 IU/L or equivalent units of human chorionic gonadotropin [HCG])

10) Inability to generate lung function data at Visit 1 meeting the minimum standards of the ATS/ERS 2005 guideline ([Miller et al. 2005](#)), as determined by central review

11) Clinically significant abnormal laboratory value at Visit 1 indicating a potential risk for the subject if enrolled in the trial as evaluated by the investigator

12) Pregnant or breast-feeding female subjects

13) Female subjects of childbearing potential not willing to use contraceptive methods as described in Section [5.3.1](#)

14) Male subjects not willing to use contraceptive methods as described in Section [5.3.1](#)

15) Subjects not willing to adhere to dietary restrictions during the trial period as described in Section [5.4](#)

16) Participation in any other interventional trial during the trial period

17) Subjects known or suspected of not being able to comply with this trial protocol (e.g. due to alcoholism, drug dependency or psychological disorder)

18) Discontinuation or change of previous antifibrotic treatment (e.g. nintedanib or pirfenidone) due to disease progression

Clinical Trial Protocol

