6.5.3 End-of-Trial (Visit 15)

Visit 15 is performed minimum 2 weeks and maximum 4 weeks after the last IMP administration.

The following procedures are performed:

- Recording of concomitant medication
- 12-lead ECG
- Blood sampling for safety and biomarker assessments (See [Table 1](#) and Section [8](#))
- Urinalysis
- Pregnancy test (beta-HCG)
- Physical examination including body weight (See [Table 1](#) and Section [8.2.4](#))
- Vital signs
- Spirometry
- Slit lamp examination
- Concomitant medication
- Reporting of AEs

If a subject is withdrawn from treatment (see Section [5.7](#)), a Visit 15 (end-of-trial visit) must be performed.

Clinical Trial Protocol

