8.2.7 Safety Laboratory Parameters

Safety laboratory parameters which are to be taken at every visit to the clinic:

- Haematology: Haemoglobin (Hb), haematocrit (erythrocyte volume fraction), platelet count (thrombocyte particle concentration [TPC]), leucocyte count, mean corpuscular volume (MCV)
- Biochemistry: Albumin, alanine transferase (ALT), aspartate aminotransferase (AST), alkaline phosphatase (ALP), bilirubin, blood urea nitrogen (BUN), calcium, creatinine, c-

Clinical Trial Protocol

Vicore Pharma AB
Trial ID: VP-C21-005

Version: 7.0
Date: 15-Sep-2021

reactive protein (CRP), gamma glutamyl transferase (GGT), glucose, lactate dehydrogenase (LD), potassium, sodium

- Urinanalysis: Dipstick for bilirubin, glucose, ketones, protein, specific gravity, urobilinogen, and pH

Any laboratory abnormality, judged by the investigator to be a clinically relevant worsening since Visit 1, should be reported as an AE if the laboratory abnormality requires clinical intervention or further investigation, unless the laboratory abnormality is associated with an already reported event.

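### Section 13.4.4 classes laboratory values only as low, normal or high and compares baseline with an off-treatment visit, so no specified output counts subjects by size of liver-test elevation

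*Combined protocol and SAP*

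**What the plan says.** Section 13.4.4 (Laboratory Safety Assessments) contains the whole laboratory analysis in the protocol. On the continuous side, "Continuous laboratory data will be summarised by visit including the change from baseline"; the statistics to be reported are not named. On the categorical side, "Laboratory parameters will be categorised as ‘low’, ‘normal’ or ‘high", that is, "below, within, or above the reference ranges, respectively) and summarised by visit and for changes from baseline to end-of-trial in a shift table".

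Section 5.2, exclusion 9, bars at Visit 1 "Increased AST or ALT >3 times Upper Limit of Normal (ULN), or bilirubin >1.5 times ULN"; the Protocol Summary says the same. Values between 1×ULN and those limits are therefore compatible with entry. Exclusion 11 adds a filter without a numeric limit: "Clinically significant abnormal laboratory value at Visit 1 indicating a potential risk for the subject if enrolled in the trial", as the investigator evaluates it.

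Section 8.2.7 has biochemistry, including ALT, AST, ALP, GGT and bilirubin, taken at every clinic visit. It also gives the adverse event rule: "Any laboratory abnormality, judged by the investigator to be a clinically relevant worsening since Visit 1, should be reported as an AE", on condition that it requires clinical intervention or further investigation and does not belong to an event already reported.

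The end-of-trial visit is off treatment: "Visit 15 is performed minimum 2 weeks and maximum 4 weeks after the last IMP administration" (section 6.5.3).

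The introduction to section 13 says that it gives the principal features and that a separate SAP will hold the detail. That SAP is not in the text available here.

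**The concern.** A three-class scale with cut-points only at the reference limits has a ceiling at 1×ULN. The entry criteria allow some subjects to start at that ceiling, and for them the scale cannot register a worsening of any size. For subjects who start within range, it registers that a limit was crossed but not by how much. The protocol treats 3×ULN (ALT/AST) and 1.5×ULN (bilirubin) as meaningful at entry, but its analysis does not use those limits.

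The shift table adds a second loss. It compares baseline with Visit 15 only, after 2–4 weeks without drug, so an on-treatment peak does not appear in it.

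Safety is the primary objective (section 4.1). Treatment lasts up to 36 weeks, whereas the Phase 1 trials described in section 3.5 dosed for up to 8 days. There is no control arm to set a background rate, so the number of subjects reaching a given elevation, and how far each rose, is much of what the laboratory data can contribute.

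**Working it through.** No stated figure has to be reproduced here. The check applies the plan's own classification rule to specific values.

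**Inputs.** High means above 1×ULN (13.4.4). Entry is allowed up to 3×ULN for ALT/AST and 1.5×ULN for bilirubin (5.2, exclusion 9). The shift table runs from baseline to end-of-trial (13.4.4), with end-of-trial 2–4 weeks after the last dose (6.5.3). The target is 60 subjects with a completed 12-week visit (6.2). The ULN-multiple bands in the last column are illustrative and not in the documents: ≤1, >1–3, >3–5, >5–10, >10 for ALT/AST; ≤1, >1–1.5, >1.5–2, >2 for bilirubin.

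**Step 1: classify pairs of values.**

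| Test | From → to (×ULN) | Ratio | Plan's classes | Illustrative bands |
|---|---|---|---|---|
| ALT/AST | 1.2 → 10 | 10/1.2 = 8.3 | high → high | >1–3 → >5–10 |
| ALT/AST | 3 → 10 | 10/3 = 3.3 | high → high | >1–3 → >5–10 |
| ALT/AST | 1.2 → 1.3 | 1.3/1.2 = 1.08 | high → high | >1–3 → >1–3 |
| ALT/AST | 3 → 1.1 | 1.1/3 = 0.37 | high → high | >1–3 → >1–3 |
| ALT/AST | 0.9 → 1.1 | 1.1/0.9 = 1.22 | normal → high | ≤1 → >1–3 |
| ALT/AST | 0.9 → 10 | 10/0.9 = 11.1 | normal → high | ≤1 → >5–10 |
| Bilirubin | 1.5 → 10 | 10/1.5 = 6.7 | high → high | >1–1.5 → >2 |

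Under the plan's rule an 8.3-fold rise, a trivial change and a clear improvement share one cell, while 0.9 to 1.1×ULN counts as a shift.

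**Step 2: follow one subject into the shift table.** Take baseline 1.2×ULN, an on-treatment peak of 10×ULN, and value v at Visit 15. If v is above 1×ULN, the entry is high-to-high. If v is within range, it is high-to-normal, which reads as an improvement. Neither entry carries the peak. The by-visit table counts the subject as high at the peak visit, as it did at baseline.

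**Step 3: the continuous summary.** One subject's change is 10 − 1.2 = 8.8×ULN. With all others unchanged, the group mean change is 8.8/n:

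- n = 60: 8.8/60 = 0.15×ULN
- n = 40: 8.8/40 = 0.22×ULN
- n = 20: 8.8/20 = 0.44×ULN

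The sample SD of change at n = 60 is 8.8/√60 = 1.14×ULN, and the maximum change is 8.8×ULN. The mean largely hides the subject, the SD hints at it, and a maximum would show it. Section 13.4.4 names none of these statistics. Section 13.2.1 names SD and range, but for baseline characteristics.

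**Step 4: other outputs.** The listings in 13.4.1 cover SAEs and AEs leading to withdrawal from treatment. AEs of special interest (9.3) are cardiac and ophthalmic. No section describes a highest on-treatment value, a ULN-multiple class, or a joint look at transaminases and bilirubin for analysis.

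**The case against.** Four points on the other side carry weight.

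- **The SAP.** Section 13 defers detail to a separate document, which may already contain graded liver tables. A reader might infer that such tables are not planned at all; the available text cannot establish that. What stands is that the protocol's own stated rule has the ceiling.
- **High-to-high throughout.** A reader might infer that any on-treatment rise in a subject who enters above ULN is recorded as no shift. The documents do not support this. The single shift table uses Visit 15, so a resolved rise appears as high-to-normal. High-to-high needs a value still above ULN 2–4 weeks after the last dose.
- **Invisibility.** A reader might also infer that a marked rise would go unseen. That goes too far. Change from baseline is summarised at every visit, and a maximum would print the rise. A 10×ULN transaminase would plausibly meet the section 8.2.7 rule and enter the AE tables, which serve the primary endpoint. The data monitoring committee reviews all available safety data at its meetings (section 6.1). These safeguards are real but partial: the statistics are unnamed, the AE rule rests on judgement and has no numeric threshold, and committee review does not define the final report.
- **Frequency.** The example is a constructed subject. The documents do not say how many subjects will enter above ULN, exclusion 11 screens out some, and nothing in the visible text marks the liver as a target organ.

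These points limit the weight of the concern. None supplies a specified output that counts subjects by size or peak of elevation.

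**Conclusion.** The point holds as a cheap improvement, not as a flaw that undermines the safety analysis. The categorical summary in 13.4.4 cannot separate a small from a large elevation above ULN, and its one shift table compares baseline with an off-treatment visit. The affected subjects are those who enter above ULN (up to 3×ULN for ALT/AST, 1.5×ULN for bilirubin), plus any who cross ULN during the trial.

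The conclusion rests on the protocol text alone; a SAP that already grades liver tests would resolve it. It does not depend on whether laboratory baseline is Visit 1 or Visit 2, which section 13 leaves undefined. The figure of 0.15×ULN assumes one affected subject among 60 and no change in the rest. No decision rule uses this table, and the underlying values are kept, so the loss lies in reporting and can be recovered.

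**What to change.** In 13.4.4, carried into the SAP before database lock:

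1. For ALT, AST and bilirubin, add classes in multiples of ULN that include the protocol's own entry limits. The sponsor chooses the higher bands, for example ≤1, >1–3, >3–5, >5–10 and >10 for ALT/AST, and ≤1, >1–1.5, >1.5–2 and >2 for bilirubin. ALP and GGT may be handled likewise with bands the sponsor defines, since exclusion 9 sets no limit for them.
2. Cross-tabulate each subject's baseline class against the highest on-treatment class, and state which visit is the laboratory baseline.
3. List subjects with ALT or AST above 3×ULN together with raised bilirubin at the same visit.
4. Keep low, normal and high for the other parameters.

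If the SAP already does this, a cross-reference in 13.4.4 is enough.

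The cost is one more table and one listing from samples already taken at every visit. Many cells will be sparse, and movement within a band (for example 1.1 to 3×ULN) will still show no shift. The change concerns tabulation only and alters no clinical management rule.
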